4.1 OVERVIEW OF STUDY DESIGN/INTERVENTION

4.2 Design

This is a single-arm Phase II trial testing the efficacy of concurrent cisplatin and radiation in breast cancer patients with measurable metastatic or locally recurrent tumor, based on HRR status as determined by the MSK-HRR assay. Prior to study enrollment, all patients will require assessment by the radiation oncologist and medical oncologist. Patients will receive a baseline PET-CT +/- MR for evaluation of the tumor to be irradiated and to assess extent of disease systemically. If unavailable within the time specifications of the study, the PET-CT +/- MR will be performed after study registration. Biopsy of the tumor to be irradiated will be performed. Fresh tissue specimens will be sent to the laboratory of [name] for performance of the MSK-HRR Assay. Results from the functional assay will be utilized towards the primary endpoint. Additional unutilized tissue will be sent to the Immune Monitoring Facility Laboratories for TIL analyses to be conducted by [name]. Bloodwork will be sent to the lab of [name] for ctDNA analyses. After the biopsy, patients will undergo simulation for palliative radiation to the tumor site. Following simulation, patient will initiate a 25 mg/m² infusion of cisplatin once a week \pm 3 days. The starting dose will depend on baseline laboratory results within 28 days prior to registration. Following 1-2 weeks of cisplatin, RT will be initiated. Weekly cisplatin (\pm 3 days) will be continued and delivered concurrently with RT. After the completion of RT, weekly cisplatin (\pm 3 days) will be continued until disease progression or until assessment of treatment response at Week 12 post RT (+/- 2 weeks), based on MD discretion. Patients whose HRR status is found to be inevaluable by the MSK assay will not be included in the study and will be replaced by eligible patients.

At Week 12 (12 \pm 2 weeks after RT; with strong recommendation at 12 weeks), repeat imaging with the same imaging methods used for baseline assessment will be performed. Treatment response will be

determined by either PRC or RECIST 1.1.

We estimate accrual will occur at the rate of 15 patients per year. It will take 3.5 years to accrue the total of 54 patients. Patients will be followed up to 24 weeks after completion of RT to determine all study endpoints. Clinical follow-up will continue until death.

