5.3 Tumor Biopsy

4 cores biopsies are required, with 2 optional cores, will be obtained from the tumor to be irradiated, with image-guidance as necessary. The safety and feasibility of the biopsy will be determined by the study Interventional Radiologist. Clip placement in target lesion is recommended if CT or MR-guided biopsy is performed. Skin metastases will be biopsied by an MSKCC surgeon, dermatologist or a radiation oncologist. The minimum core length is 6 mm. One out of the 4 cores will be fixed in 10% neutral buffered formalin and sent to Pathology for routine diagnostic confirmation of triple negative breast cancer, prior to irradiation. The remainder of the cores will be placed in a 1 mL freezer vial in DMEM standard medium at room temperature with regular ice on top of the specimens and transported directly to [name] laboratory for the MSK-HRR assay. If there is any remaining tissue left after the MSK-HRR assay, DNA will be extracted and stored in [name] lab for possible future analysis. The estimated turn-around time for functional assay, from receipt of tissue to interpretation, is 5 business days. However, the results of the assay (determining HR-proficient vs HR-deficient) status are not necessary for patients in order to receive the study treatment and will only be shared with the study statistician and primary investigator, for the purposes of confirming which patients can remain on study (i.e. they must have a definitive HRR repair status). Patients who are unable to obtain a definitive HRR status will be excluded from analysis of the primary endpoint of the study, but will be counted towards the secondary and exploratory objectives of the study.

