13.0 CRITERIA FOR REMOVAL FROM STUDY

Participants will be removed from the protocol for any of the following reasons:

- Development of disease progression that warrants a change in the radiation or chemotherapy treatment plan or an alternative therapy.
- Any grade 4 non-hematologic toxicity, except in cases where the treating physician believes the patient is deriving benefit from remaining on the study.
- Chemotherapy treatment delay of 3 consecutive weeks for any reason
Note: Disruption to the cisplatin treatment schedule for 3 weeks due to unforeseen circumstances, holidays or the patient being on vacation is permitted and will be reviewed on a case-by-case basis.
- For safety reasons, the investigator considers it to be in the best interest of the participant that they be withdrawn
- The patient wishes to withdraw from the study
- HRR status is unable to be obtained from the core biopsy taken at the beginning of the study.

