However, we will plan to accrue a total of **62** patients in order to allow for early dropout due to disease progression/death prior to response evaluation, or inability to obtain HRR status from the core biopsy. For the primary analysis, all patients for whom HRR status can be ascertained will be included in the denominator. Patients who progress or die prior to the response evaluation at 12 +/- 2 weeks post-RT will be included as failures. This includes patients with disease progression outside of the irradiated tumor. Patients for whom HRR status cannot be ascertained or who left the study for nondisease related reasons will be replaced.

A secondary analysis of interest is to evaluate the CR rate among the subset of patients who are able to complete the planned study treatment and have a scan at the 12 +/- 2 week post-RT time point. Radiographic complete response (CR) of the irradiated tumor will be counted as a positive response to treatment. Radiographic response less than a CR, progression of the irradiated tumor or appearance of a new lesion within the radiated field will be categorized as a failure to respond to treatment. All other sites of metastatic disease that is outside of the irradiated field will be monitored and counted toward disease progression.

Based on prior experience with the HRR assay, we estimate that approximately 10% of patients will either 1) not have a definitive HRR status, or 2) will not complete the planned study treatment or 3) not have a response assessment at 12-14 week time point. To ensure we have 80% power for both the primary and secondary analyses we have added 8 patients to the sample size for a total of 62. The accrual number has been adjusted to 54 patients.

We expect to accrue 1 to 2 patients per month, or approximately 18 patients per year. Thus, accrual for the trial will be completed in 3.5 years. Based on previous data on the tolerability of cisplatin and radiation extrapolated from head and neck and gynecologic malignancies, we do not anticipate toxicities associated with the study treatment and as such, we have not incorporated an early stopping rule.

Secondary endpoints include overall response rates (CR+PR+stable disease), time to progression and CTCAE v4.0 toxicities. These endpoints will be compared by HRR status using the log-rank test for time-to-event endpoints and Fisher's exact test for binary endpoints.

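### Patients without a definitive HRR status are outside the study in 4.2, removed in 13.0 and counted for secondary aims in 5.3, and 14.0 gives them no analysis population

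*Combined protocol and SAP*

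**What the plan says.** Four sections of the combined protocol and SAP deal with the patient whose biopsy yields no definitive HRR status.

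- **4.2 Design:** "Patients whose HRR status is found to be inevaluable by the MSK assay will not be included in the study"; the same sentence has them replaced.
- **5.3 Tumor Biopsy:** such patients "will be excluded from analysis of the primary endpoint of the study, but will be counted towards the secondary and exploratory objectives of the study". The sentence before gives a different signal: results go to the statistician and the principal investigator for "confirming which patients can remain on study (i.e. they must have a definitive HRR repair status".
- **13.0 Criteria for Removal from Study:** the lead-in is "Participants will be removed from the protocol for any of the following reasons", and one listed reason is "HRR status is unable to be obtained from the core biopsy taken at the beginning of the study".
- **14.0 Biostatistics:** "Patients for whom HRR status cannot be ascertained or who left the study for nondisease related reasons will be replaced". Nothing is said about their toxicity, response or progression data. The secondary endpoints (overall response, time to progression, CTCAE toxicities) are to be compared by HRR status, and no other analysis of them is given.

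**The concern.** The rules cannot all be applied to one patient. A patient who is not in the study cannot also count towards its secondary aims. The section that should settle the matter, 14.0, speaks only of replacement.

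This would be a paper problem if the assay result always came before treatment, but the plan does not require that. A treated patient could therefore leave the toxicity and progression results because of a laboratory failure, and two analysts following different sections would report different denominators. Toxicity of concurrent cisplatin and radiation is a stated secondary objective (2.0), so it should be clear which treated patients it describes.

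**Working it through.** **1. Can such a patient already have been treated?** Section 5.3 gives an assay turnaround of 5 business days from receipt of tissue and says the result is not needed for treatment. Section 8.1 allows the biopsy after registration, before the first cisplatin dose. Section 4.3.1 lets cisplatin start straight after simulation. So yes, some can. Section 8.1 also allows the biopsy within the 28 days before registration, so others may be known to be inevaluable before any dose. The documents do not give the split.

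**2. What each section implies for a treated patient without a status.**

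| Section | In the study? | Primary analysis | Toxicity, response, progression |
|---|---|---|---|
| 4.2 | No | Out, replaced | Out, by implication |
| 5.3 | Must have a status to remain | Out | In |
| 13.0 | Removed from protocol | Not stated | Not stated |
| 14.0 | Not stated | Out, replaced | Not stated; no group in the by-HRR comparison |

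The primary-analysis column is consistent wherever it is filled. The last column is not.

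**3. Would the data exist?** Section 9.0 ends routine visits at removal or death, so a patient removed early may have no week-12 scan and no later progression assessment under the protocol. Other provisions continue: toxicity assessment to progression or death (11.1), SAE reporting to 30 days after the last treatment (17.3), and clinical follow-up to death (4.2). No text says which applies after removal for this reason.

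**4. Could 5.3 be carried out under 14.0?** For the exploratory analyses, yes. Immune and ctDNA markers against response, and PRC against RECIST agreement, need no HRR group, provided that the response scan exists. For the secondary endpoints, no. The only specified analysis is by HRR status, and no all-treated summary is defined.

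**5. How many patients?** Section 14.0 allows about 10% for three reasons together: no definitive status, treatment not completed, or no response assessment. Taken as a ceiling on the first reason:

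- 0.10 × 54 = 5.4, about 5 patients
- 0.10 × 62 = 6.2, about 6 patients

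Both totals appear in 14.0, which ends with accrual adjusted to 54. No separate assay-failure rate is given.

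**6. Illustration, with assumed counts.** Suppose that 5 of 54 treated patients are dropped and 10 of the remaining 49 have a severe toxicity.

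- Reported rate: 10/49 = 20.4%
- All-treated rate if none of the 5 had one: 10/54 = 18.5%
- All-treated rate if all 5 had one: 15/54 = 27.8%

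The reported rate can be too high or too low. The ends of the range are extremes and not expectations.

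The power table in 14.0 concerns the primary comparison, from which these patients are excluded in any case, so this point does not rest on it.

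**The case against.** The best defence is that removal from protocol is not an analysis rule. Section 13.0 also removes patients whose progression warrants a change of treatment, yet 14.0 keeps those who progress before the response scan in the primary denominator as failures. Read this way, 13.0 and 5.3 fit together: the patient goes off protocol, and the data already obtained still count. That stands, and a reader who infers from 13.0 alone that these patients are excluded from analysis goes further than the text. It does not rescue the clause in 4.2, and it does not give these patients a place in 14.0.

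Three stronger readings are tempting and are not supported.

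- **That the data 5.3 needs would never be collected.** Baseline data and events up to removal would exist, and 11.1, 17.3 and 4.2 keep some follow-up going. The exposed items are the week-12 scan and later progression data.
- **That toxicity would be understated, which is worse because there is no stopping rule.** Dropping a patient changes numerator and denominator together, and nothing in the documents links assay failure to toxicity. SAEs remain reportable, and 16.3 describes institutional monitoring of phase II trials. The missing stopping rule is a separate matter.
- **That 5 or 6 treated patients will be lost.** That figure assigns the whole pooled allowance to assay failure and assumes every such patient was dosed. Patients found inevaluable before any dose can be left out and replaced without harm to the toxicity results.

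**Conclusion.** The inconsistency is real and is in the current text. Section 4.2 conflicts with 5.3, 5.3 sits uneasily with its own preceding sentence and with 13.0, and 14.0 defines no population in which these patients' toxicity, response and progression could be summarised. Some of them may have been treated. Under 4.2 they leave those results; under 13.0 with 9.0 their week-12 and later data may be missing.

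The effect is modest. It falls on secondary and safety results, with an expected ceiling of about 5 of 54 (6 of 62), and the true number is probably smaller because the 10% pools three reasons. The direction of any bias is unknown. The ceiling assumes that the plan's own loss allowance is right. The primary analysis is not in dispute. The change is worth making because it is cheap and the sections cannot be followed together as written.

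**What to change.** Reconcile 4.2, 5.3, 13.0 and 14.0, and state the following once in 14.0 for the other sections to refer to:

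- All patients who receive any study treatment are in the overall toxicity, response and time-to-progression summaries, reported in addition to the comparisons by HRR status.
- Patients without a definitive HRR status are left out only of the primary analysis and of comparisons by HRR status, and are replaced for the primary analysis.
- Collection of outcome and toxicity data continues after removal for this reason, with 9.0 and 11.1 brought into line.

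The analysis population can be defined without deciding whether protocol treatment continues for these patients; that is for the sponsor to reconcile across 4.2, 5.3 and 13.0. It would also help to report how many patients had no definitive status, and how many of those had been treated.

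The cost is wording, plus data follow-up of a few patients already treated.

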4.3 Intervention

4.3.1 Cisplatin Administration

Cisplatin treatment should be initiated following study registration. The starting dose of cisplatin is established as 25 mg/m² ivpb once a week (\pm 3 days) for 1-2 weeks prior to radiation. Dose modification following the first dose of cisplatin is subject to the discretion of the treating physician. Dosing calculation guidelines will follow MSKCC policies described on the website:

http://mskweb5.mskcc.org/intranet/shared/pharmacy/guidelines/Chemo_Guidelines/Manuals/Cisplatin.html

Cisplatin may be initiated immediately following simulation but prior to first radiation fraction. The rationale is so that the patient may initiate a form of treatment while waiting 1-2 weeks for radiation treatment planning to be completed.

Cisplatin may cause myelosuppression or other known non-hematologic toxicities. Following the completion of RT, pending no toxicities, but prior to the week 12 post RT evaluable timepoint, patients will continue to receive cisplatin based on MD discretion, or until POD.

The starting (first) dose of cisplatin will be 25 mg/m² ivpb once a week (\pm 3 days). Following the first dose of cisplatin, a CBC will be drawn once a week (\pm 3 days) prior to treatment to ensure treatment parameters are met. A comprehensive panel and Mg++ level will be obtained on D15 (\pm 3 days) of every cycle of cisplatin; these values will inform the dose for the following cycle of cisplatin. The length of one cycle of Cisplatin is 21 days. If cisplatin is withheld, the cycle count for treatment is also held. Based on the laboratory values drawn from the prior week's bloodwork, if the following parameters are met, cisplatin should be held as directed.

- If ANC is <1,000 mcL and/or platelets are <100,000 mcL, withhold cisplatin therapy for one week and repeat measurements. Physicians have the option of administering growth factor support during the time when ANC < 1,000 mcL or platelets are < 100,000 mcL. The treating MD may modify the subsequent cisplatin doses at their discretion. If there is a delay of 3 consecutive weeks of treatment due to toxicity, then the patient must discontinue protocol therapy and be removed from the study.
- If the ANC is still <1,000 mcL or platelets are 75,000-99,000 mcL, then hold weekly cisplatin again until the ANC is >1,000 mcL and platelets are >100,000 mcL. The treating MD may modify the subsequent cisplatin doses at their discretion.
- If serum creatinine is >1.5 mg/dL, delay treatment, provide intravenous hydration and check 12 or 24 hour creatinine clearance, serum creatinine and electrolytes after 24 hours. If the serum

creatinine is ≤ 1.5 mg/dL and creatinine clearance ≥ 60 cc/min, may give full dose of cisplatin. If serum creatinine is 1.6-1.9 and creatinine clearance is between 30-60 cc/min, cisplatin can be given at the discretion of the treating physician. If serum creatinine is >2 OR creatinine clearance is <30 cc/min, hold cisplatin.

- If the patient develops any non-hematologic grade 3-4 toxicity, cisplatin will be held until toxicity is reduced to grade 2 or less. Dose reduction is permitted at the discretion of the treating physician. If a patient experiences grade 2 toxicity (with exception of alopecia) that lasts >2 weeks, cisplatin will be held and dose reduction recommended at discretion of the treating physician. Cisplatin will be discontinued if greater than grade 2 toxicity persists following 2 dose reductions.
- If the patient develops an intercurrent illness (e.g. infection) that, in the opinion of the treating medical oncologist, mandates a delay of cisplatin therapy, the intercurrent illness must be resolved within a time frame such that no more than 2 weekly doses of cisplatin are withheld. If therapy must be withheld for a longer period of time, the patient will be removed from the study.
- Following the completion of RT but prior to the week 12 post RT evaluable timepoint, patients will continue receiving cisplatin based on MD discretion. The dose and schedule of cisplatin after the completion of RT will be at the discretion of the treating MD. If there is a delay of 3 consecutive weeks of treatment, then the patient must discontinue protocol therapy and will be removed from study. Continuation of cisplatin and the dose and schedule of cisplatin after Week 12 post RT assessment will be at the discretion of the treating MD.
- Note: Disruption to the cisplatin treatment schedule for 3 weeks due to unforeseen circumstances, holidays or the patient being on vacation is permitted and will be reviewed on a case-by-case basis.

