³ Radiation dose will be $250 \text{ cGy} \times 15 \text{ fx} = 3750 \text{ cGy}$ to the metastatic site delivered in 3 weeks for metastatic disease or $200 \text{ cGy} \times 25 \text{ fx} = 5000 \text{ cGy}$ delivered in 5 weeks to the chest wall, breast and/or regional lymph nodes, plus an optional 10-14 Gy boost to areas of gross tumor, for non-metastatic/locally recurrent disease.

⁴ The length of one Cisplatin cycle is 21 days. If cisplatin is withheld, the cycle count for treatment is also held.

⁵ Cisplatin will be once a week (± 3 days). The dose of cisplatin can be reduced in the event of toxicities defined in Section 4.2.1.

⁶ Following the completion of RT, pending no toxicities, but prior to the week 12 post RT evaluable timepoint, patients will continue to receive cisplatin or until POD, based on MD discretion.

⁷ At 12 ± 2 weeks after RT, all patients will receive PET-CT for treatment response and/or staging. MR will also be obtained if the patient had an MR at baseline.

⁸ PET-CT +/- MR will occur at 12 ± 2 weeks after RT. PET/CT +/- MRI q6 months after RT is recommended but not required.

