9.0 TREATMENT/ INTERVENTION PLAN

During radiation therapy, patients will undergo a physical exam and evaluation by a radiation oncologist once a week for toxicities in a status check visit as per current standard practice.

While receiving cisplatin, patients will be followed by a medical oncologist, who will obtain complete blood count once a week and serum chemistries with Mg²⁺ on D15 (± 3 days) of every cycle of cisplatin therapy. The medical oncologist will evaluate the patient on D1 of every cycle of cisplatin therapy. The length of one cycle of Cisplatin is 21 days.

Following the completion of RT, pending no toxicities, but prior to the week 12 post RT evaluable timepoint, patients will continue to receive cisplatin or until POD, based on MD discretion.

At Week 12 (12 ± 2 weeks after completion of radiation therapy), patients will be seen either by a radiation oncologist or a medical oncologist, and then every 6 months for routine follow-up visits either by a radiation oncologist or medical oncologist, until removal from study or death. Peripheral bloods and blood banking research samples (ctDNA) be collected at baseline, at the end of RT and at the 12 ± 2 week assessment point. Follow-up imaging studies (PET-CT +/- MRI) will be obtained at 12 ± 2 weeks after RT. PET/CT +/- MRI of the target lesion q6 months afterwards will be recommended but not required.

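### A three-week cisplatin delay takes the patient off study, possibly before the primary scan, and 14.0 does not say whether a replaced patient with known HRR status is still counted

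*Combined protocol and SAP*

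**What the plan says.** **Removal rules.** Section 4.3.1 has three. For low blood counts, the consequence follows a "delay of 3 consecutive weeks of treatment due to toxicity, then the patient must discontinue protocol therapy and be removed from the study". For intercurrent illness, no more than two weekly doses may be withheld: "If therapy must be withheld for a longer period of time, the patient will be removed from the study". For the period after RT and before week 12: "If there is a delay of 3 consecutive weeks of treatment, then the patient must discontinue protocol therapy and will be removed from study". Section 13.0 lists as a removal criterion "Chemotherapy treatment delay of 3 consecutive weeks for any reason".

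**Exception.** A note in both sections softens this, case by case: "Disruption to the cisplatin treatment schedule for 3 weeks due to unforeseen circumstances, holidays or the patient being on vacation is permitted". Toxicity is not among the listed reasons.

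**Follow-up after removal.** Section 9.0 describes the week-12 visit and then six-monthly routine visits "until removal from study or death". A separate sentence there schedules imaging at 12±2 weeks without conditions. Footnote 7 of the schema in 1.0 says that at that time "all patients will receive PET-CT for treatment response and/or staging", and 4.2 says "Clinical follow-up will continue until death".

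**Analysis.** Section 14.0 reads the primary endpoint at 12±2 weeks after RT. It includes in the denominator every patient whose HRR status can be ascertained, and counts as failures those who progress or die before the evaluation. It replaces patients without an HRR status and those who leave for reasons unrelated to disease. A secondary analysis is limited to patients who complete treatment and have the scan.

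**The concern.** A stop in drug treatment is turned into an exit from the study. The primary endpoint is a single imaging assessment some three months after RT, so a patient who has completed RT but had cisplatin held for neutropenia or renal toxicity may leave before the one observation that matters.

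Such a patient, alive and unprogressed with known HRR status, meets two rules in 14.0 at once: the denominator rule keeps the patient and the replacement rule brings in a substitute. Nothing says whether the original patient remains in the count. If so, no outcome is stated, because the failure rule covers only progression and death.

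Two things are at stake. Outcomes may be lost for a reason that arises after enrolment and is related to treatment, so that replacement tilts the analysed set toward patients who tolerate cisplatin. And analysts could build different primary sets from the same text, with the choice open until results are known.

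**Working it through.** **1. Can removal precede the scan?** The window is weeks 10 to 14 after RT. A delay starting at the end of RT is complete at week 0 + 3 = 3, which is 10 − 3 = 7 weeks before the window opens. A delay starting before week 7 is complete before week 10; one starting at week 7 is complete as the window opens. The toxicity rule can also apply before or during RT. So removal can come first.

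**2. The plan's own power.** Inputs from 14.0: N = 54, CR 65% (deficient) and 30% (proficient), one-sided 5%, HRR-deficient share 40%, 35% or 30%. The unpooled formula is power = Φ(0.35/√[0.30×0.70/n_P + 0.65×0.35/n_D] − 1.645). At 40%, n_D = 21.6 and n_P = 32.4, so the standard error is 0.1304 and power = Φ(2.683 − 1.645) = 85.0%. The other shares give 83.2% and 80.4%. The stated 85%, 83% and 80% are reproduced.

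**3. Illustrative removals.** No delay rate is given. Section 14.0 estimates about 10% for unknown HRR status, incomplete treatment and missing assessment together; 10% × 54 = 5.4. I assume 5 removals, as an illustration rather than a bound, with 22 deficient and 32 proficient patients and removal unrelated to would-be response.

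With d deficient and p proficient removals counted as non-CR, the expected difference is 0.65(22 − d)/22 − 0.30(32 − p)/32.

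- No removals: 65.0 − 30.0 = 35.0 points.
- d = 2, p = 3: 59.1 − 27.2 = 31.9 points.
- Replaced or left out: 35.0 points under the same assumption.

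Section 14.0 names no primary test. Power by full enumeration, using a one-sided 5% pooled z-test as an assumption:

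| Handling of the 2/3 split | Power |
|---|---|
| No removals, or full replacement | 83.4% |
| Left out, not replaced (20 vs 29) | 79.8% |
| Counted as non-CR (22 vs 32) | 78.0% |

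The 83.4% baseline differs from the plan's 85% because of the test, not because of removals. With the unpooled formula and 10% removed in each group, the corresponding figures are 85.2% (replaced), 81.8% (left out) and 77.6% (non-CR).

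**4. One-sided clustering.** If all 5 removals were deficient, the difference under non-CR coding would be 50.2 − 30.0 = 20.2 points; if all were proficient, 65.0 − 25.3 = 39.7 points. If removal is unrelated to HRR status, the chances are C(22,5)/C(54,5) = 0.8% and C(32,5)/C(54,5) = 6.4%. These show how the arithmetic behaves; they are not forecasts.

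**The case against.** The best defence is that 14.0 does deal with these patients: leaving for toxicity or illness is a reason unrelated to disease, so they are replaced. The same sentence covers patients without an HRR status, who are outside the primary analysis, which suggests that replaced means not counted. On that reading the expected difference stays at 35.0 points and power at 83%, provided removal is unrelated to response. The aim is to predict response to cisplatin plus RT, the trial has one arm and no randomization to protect, and replacing patients who cannot take the treatment is a defensible choice.

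Much of this stands. A reader might infer that these patients have no disposition at all; the replacement rule gives them one. What it leaves unsettled is the conflict with a denominator that takes in everyone with ascertained HRR status. The separate completer analysis also suggests that the primary set was meant to keep non-completers.

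A reader might also infer that the scan is certainly lost. The documents do not establish that: 9.0 attaches the removal limit to the visits, while its imaging sentence, schema footnote 7 and 4.2 point toward continued assessment. Loss is possible, not shown.

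The post-RT rule is the weakest trigger, since 4.3.1 leaves continuation, dose and schedule after RT to the treating physician; a deliberate stop or longer interval need not be a delay. The toxicity and illness rules are firmer.

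Finally, the large swings under one-group clustering might be read as evidence of bias between HRR groups. No mechanism for clustering is documented, and 5.3 restricts HRR results to the statistician and primary investigator.

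**Conclusion.** The point holds in a limited form and should be addressed. The plan removes patients from study for a toxicity or illness delay that can be complete before the primary scan, leaves their later imaging unclear, and permits two primary sets: one that keeps replaced patients with known HRR status and one that drops them. For those kept without a scan, progression or death, no outcome is stated.

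The likely numerical effect is modest. With 5 assumed removals split 2/3, the expected difference is 31.9 rather than 35.0 points under non-CR coding, and pooled-z power is 78%, or 80% if the patients are left out, against 83%. This rests on an assumed removal count, an assumed test and removal unrelated to response. The main reason to act is that the primary set and outcome should be settled before results are known. Confidence is medium, because the frequency of such delays cannot be taken from the documents.

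**What to change.** **Sections 4.3.1 and 13.0.** State that a cisplatin delay, and any other treatment stop without progression, such as one for grade 4 non-hematologic toxicity, ends protocol cisplatin only. Unless consent is withdrawn, the patient stays on study and has the scan already scheduled at 12±2 weeks. With known HRR status, the patient stays in the primary denominator and is not replaced.

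**Section 14.0.** Limit replacement to patients without a definitive HRR status. Count patients with known HRR status and no scan as non-CR. Say in advance how a scan taken after new systemic therapy counts, for example as non-CR with a sensitivity analysis.

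**Cost.** Wording only: no new visit or procedure, and the safety rules for stopping cisplatin are unchanged. Expected power is somewhat lower than under full replacement (78% against 83% in the illustration). Some patients with reduced cisplatin exposure enter the primary set; the completer analysis in 14.0 already addresses that.
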